7.3.1 Risks of EVT

EVT related risks are diverse. Potential complications include, but are not limited to: air embolism, hematoma or bleeding at the puncture site, infection, distal embolization, vasospasm, thrombosis, dissection or perforation, embolus fragmentation, acute vessel closure, ischemia, intracranial hemorrhage, pseudoaneurysm formation, neurological deficits including stroke, and death.

7.3.2 Benefits of EVT

Participants should understand that the treatments offered in this study are currently recognized as effective and beneficial. However, based on prior research, it remains unclear which of the two commonly used clinical strategies—IVT followed by EVT or EVT alone—achieves better vascular recanalization rates and clinical outcomes.

7.3.3 Potential risks and benefits to participants

Participants in the IVT followed by EVT group will receive standard medical therapy available at their healthcare facilities. Intravenous rtPA is an approved and evidence-based treatment for posterior circulation stroke, and some patients in this trial may receive intravenous rtPA. Due to the more detailed follow-up plan of BEST-BAO compared to the current guidelines, participants in this trial may need to undergo more follow-up imaging or neurological examinations (such as 24–72 hour imaging, 90±14 day mRS scores, etc.) than those who are not enrolled. The risks associated with these imaging and neurological function tests are acceptable, and participants may benefit more from these additional examinations.

7.3.4 Risk-benefit ratio

The primary aim of this trial is to determine the efficacy and safety of IVT followed by EVT versus EVT alone for AIS-BAO. Previous non-randomized studies, including retrospective and cohort analyses, have shown inconsistent conclusions. Due to limitations in their designs, the differences in efficacy and safety between these two treatment strategies remain unclear. Regardless of which treatment strategy is ultimately proven superior, this trial will represent a significant benefit for all patients with AIS-BAO. Even if the two strategies are proven to be equivalent in efficacy and safety, this finding will guide clinical practice by emphasizing the focus on EVT itself, simplifying emergency workflows, increasing the proportion of patients receiving timely treatment, reducing the burden on healthcare systems, and ultimately benefiting a greater number of patients.

8. Methods

8.1 Study endpoints

8.1.1 Primary endpoint

The primary endpoint of this trial is the proportion of patients achieving a mRS score ≤ 2 at 90±14 days after stroke onset. The mRS is the preferred parameter for assessing disability in stroke-related clinical trials. It is an ordinal scale with 7 levels, ranging from 0 to 6, where a score of 6 indicates death (**Appendix 1**). Using the standardized reports, mRS assessments will be conducted by trained and independent investigators and evaluators who are blinded to the assigned groups and the actual treatments received.

8.1.2 Secondary endpoints

The secondary endpoints are as following:

- (1) Proportions of patients with mRS = 0 or 1 at 90±14 days after stroke onset.
- (2) Proportions of patients with mRS = 0–3 at 90±14 days after stroke onset.
- (3) mRS score at 90±14 days after stroke onset.
- (4) NIHSS score (**Appendix 2**) at 18–24 hours after procedure, 24–74 hours after procedure, and 5–7 days after stroke onset and their changes from baseline.
- (5) Proportion of patients with a NIHSS score = 0 or 1, a NIHSS score = 0–2, a NIHSS score improvement ≥ 4 points, and a NIHSS score improvement ≥ 8 points. at 18–24 hours after procedure, 24–74 hours after procedure, and 5–7 days after stroke onset.
- (6) Glasgow coma scale score (GCS; **Appendix 3**) at 18–24 hours after procedure, 24–74 hours after procedure, and 5–7 days after stroke onset and their changes from baseline.
- (7) Barthel Index score (BI; **Appendix 4**) and the proportion with BI = 95–100 at 30±7 and 90±14 days after stroke onset.
- (8) EQ-5D-5L score (**Appendix 5**) at 90±14 days after stroke onset.

- (9) eTICI score (**Appendix 6**) and successful reperfusion rates before and after EVT.
- (10) mAOL score (**Appendix 7**) and recanalization rates at 24–72 hours after procedure.
- (11) PC-ASPECTS score (**Appendix 8**) at 24–72 hours after procedure and 5–7 days after stroke onset.
- (12) Lesion volume based on quantitative imaging detection at 24–72 hours after procedure and 5–7 days after stroke onset.

8.1.3 Safety endpoints

The safety endpoints include:

- (1) All-cause mortality within 7, 30±7, and 90±14 days after stroke onset.
- (2) Proportions of patients with intracranial hemorrhage and symptomatic intracranial hemorrhage (**Appendices 9–11**) at 24–72 hours after procedure and 5–7 days after stroke onset.
- (3) Proportions of patients with new regional cerebral embolisms during EVT (**Appendix 12**).
- (4) Proportions of patients with new cerebral infarction at 24–72 hours after procedure and 5–7 days after stroke onset.
- (5) EVT procedure-related complications within 90±14 days after stroke onset.
- (6) Other serious adverse events within 90±14 days after stroke onset.

8.1.4 Additional study parameters

Baseline parameters to be recorded include demographic data such as age, sex, ethnicity, and body mass index, as well as clinical histories, including prior stroke, comorbidities (e.g., hypertension, diabetes, atrial fibrillation, and myocardial infarction), smoking, alcohol consumption, prior medications (e.g., antiplatelets and anticoagulants), and vital signs (e.g., blood pressure, temperature, pulse, and respiration rate). Neurological assessments include pre-stroke mRS, NIHSS, and GCS scores. Clinical laboratory tests include INR, APTT, platelet count, and blood glucose levels. Imaging results will include PC-ASPECTS, PMI (Pons-midbrain index; **Appendix 13**), PC-CS (Posterior circulation collateral score; **Appendix 14**), and BATMAN (Basilar artery on CT angiography; **Appendix 15**) scores.

We will document the actual dose, type, route, and administration time of IVT medications. Additionally, we will record the time intervals from symptom onset to emergency department arrival, CT/MR/DSA imaging, randomization, IVT initiation, EVT procedure initiation, reperfusion, and EVT procedure completion. Details of endovascular devices, including model, specifications, quantity, and usage sequence, as well as type of anesthesia and sedatives (if used), will also be recorded.

Patients included in this trial are recruited from two main pathways: (1) direct referrals from external healthcare facilities and (2) direct admissions to the comprehensive stroke center (Mothership model). This recruitment strategy reflects typical clinical practice and ensures the inclusion of a diverse patient population.

8.1.5 Assessments of Clinical Outcomes

Using a standardized questionnaire, assessment of the mRS score at 30 ± 7 and 90 ± 14 days is performed by local trained investigators who are not aware of treatment allocation based on a standardized process of telephone or in-person interview. If a patient is unavailable or unable to answer the questions, a proxy or healthcare provider will be interviewed. These assessment processes must be recorded, either through audio or video. Written reports and the corresponding audio and video of the interviews will be sent to the independent endpoint adjudication committee who are also blinded for treatment allocation. The mRS score will be determined after review of these reports. If there is disagreement between the two observers, a third independent observer, who is also blinded, will resolve differences in interpretation.

Assessment of the EQ5D-5L and BI scores at 30 ± 7 and 90 ± 14 days is performed by local trained investigators who are not aware of treatment allocation based on a standardized process of telephone or in-person interview.

These assessment processes must be recorded, either through audio or video.

Assessment of the mRS, NIHSS, GCS scores at 18-24 hours, 24-72 hours, and 5-7 days is performed by local trained investigators who are not aware of treatment allocation based on a standardized process of in-person interview. These assessment processes must be recorded through video.

Video recording of the processes of assessing mRS, NIHSS, GCS at baseline is required. Video recording of the patients' baseline neurological assessment is obtained in order to allow for an independent team of investigators to confirm the satisfactory fulfillment of all inclusion/exclusion criteria.

To ensure the data quality, an independent CRO will perform 100% data verification for all centers, investigator meetings will be organized frequently to provide feedback and to discuss potential avenues for improvement, and all local trained investigators are required to receive both on-site and web-based video training.

8.1.6 Assessments of Radiological Imaging

All radiological imaging will be assessed by an independent imaging adjudication committee blinded to treatment allocation. All independent imaging adjudication committee members are required to be trained and tested before the official reading in order to reduce reader variability and increase reliability. The independent imaging adjudication committee is consisted of a CT/CTA team, MRI/MRA team and DSA team. All imaging will be read by two independent readers and a consensus reading will be performed by a senior reader of each team in case of discrepancies.

PC-ASPECTS score, infarction in new territory, and cerebral hemorrhages are determined by means of CT or MRI-DWI. PC-CS, BATMAN, and mAOL scores are determined by means of CTA, MRA, or DSA. Embolization to new territory and eTICI score are determined by means of the angiograms during EVT procedures. Lesion volume is assessed by an automated, validated algorithm. Cause of stroke is determined according to assessments of the angiograms in combination with medical records. In addition, the DSA team will review all series and images captured during EVT to determine the procedure related complication

8.2 Randomization, blinding, and treatment allocation

The randomization process will use a web-based randomization system. Patients can be randomized (**Appendix 16**) when AIS-BAO is confirmed by CTA, MRA, or DSA.

Before a patient is registered in the study database, assigned groups and treatment allocation will remain inaccessible, and patients cannot be excluded from the study after the allocation is revealed. Both patients and treating physicians will be aware of the assigned treatment group. However, trained investigators, who are blinded to assigned groups and treatment allocation, will record endpoint-related information using standardized forms and procedures, and details of the interviews. These trained evaluators will assess mRS outcomes and evaluate neuroimaging results in a blinded manner. Information related to assigned groups and treatment allocation will be maintained separately from the study database. The SC will not be informed of interim analysis results on the efficacy and safety. Independent trial statisticians will combine treatment allocation data with study database for reporting to the DSMB.

8.3 Study procedures

Patients will undergo evaluations of vital signs, mRS, NIHSS, and GCS at baseline, 18–24 hours after procedure, 24–72 hours after procedure, and 5–7 days after stroke onset. These evaluations are also routine clinical practices and will be conducted by certified investigators.

At baseline, patients will undergo CT/CTA, MRI/MRA, or CT/DSA tests to assess infarct size, vascular lesion location and extent, and collateral circulation. During the EVT procedure, vascular recanalization, reperfusion, and new regional embolism will be evaluated, along with documentation of procedural details. At 24–72 hours after procedure, patients will undergo CT/CTA or MRI/MRA tests to evaluate infarct size, vascular recanalization, and

intracranial hemorrhage. At 5–7 days after stroke onset, patients will undergo a CT or MRI test to assess infarct size and intracranial hemorrhage.

Additionally, patients will undergo evaluations of mRS, BI, and EQ-5D-5L at 30±7 days and 90±14 days after stroke onset.

Detailed trial flowcharts and visit schedules are presented in **Appendices 16 and 17**.

8.4 Withdrawal of individual participants

Participants can withdraw from the trial at any time and for any reason without any consequence. Investigators can also decide to withdraw a participant due to urgent medical reasons. Data from patients who do not provide consent for further participation will be anonymized and used for baseline analysis to better describe the study population. Missing data, including the final mRS score, will be addressed using statistical methods during analysis. Critical parts of personal data will be removed.

8.5 Premature termination of the trial

The study will only be prematurely terminated if recommended by the DSMB or required by the Ethics Committee (EC), NMPA, or other regulatory authorities. If the study is terminated early, the database will be locked after the last enrolled patient completes their 90-day follow-up, and study results will be reported.

9. Safety reporting

9.1 Temporary suspension for participant safety

If there is sufficient evidence that continuing the study may harm participants' health or safety, the sponsor will suspend the trial. The sponsor will inform the EC of any delays caused by the suspension, including the reasons for taking such action. The trial will remain suspended until further review by the EC. Investigators must notify all participants accordingly.

9.2 Definitions

9.2.1 Definition of adverse events

An adverse event (AE) is any untoward medical occurrence in a patient or clinical investigation subject administered a pharmaceutical product and which does not necessarily have to have a causal relationship with this treatment. An AE can therefore be any unfavorable and unintended sign (including an abnormal laboratory finding, for example), symptom or disease temporally associated with the use of a medicinal product, whether or not considered related to the medicinal product.

Therefore, an AE may be: A new illness; The worsening of a concomitant illness; An effect of vaccination, including the comparator; A combination of the above.

Pre-existing medical conditions are not to be reported as AEs. However, if a pre-existing condition worsens in frequency or intensity, or if in the assessment of the treating physician there is a change in its clinical significance, this change should be reported as an AE (exacerbation). This applies equally to recurring episodes of pre-existing conditions (e.g., asthma) if the frequency or intensity increases post-randomization.

9.2.2 Definition of serious adverse events

A serious adverse event (SAE) is any untoward medical occurrence that at any dose: Result in death; Are life-threatening; Require or prolong inpatient hospitalization; Result in persistent or significant disability/incapacity, or; Are a congenital/birth defect.

A SAE can also be an important medical event that may not result in death, be life-threatening, or require

hospitalization, but may jeopardize the subject and may require medical or surgical intervention to prevent one of the outcomes listed in this definition. For example, any new diagnosis of cancer (made after study enrollment) is considered an important medical event. Because our primary safety endpoints for the trial are also SAEs by definition, they will be reported dually as SAEs and as endpoints. SAEs should be managed according to the best current standard of care.

All deaths occurring during the follow up to day 90±14 will be reported as an SAE. When reporting a death, the event or condition that caused or contributed to the fatal outcome should be reported as a single medical concept.

AE occurring within 30±7 days of randomization and all SAEs will be reported in the Case Report Form (CRF). Severity and relationship definitions are presented below.

9.2.3 Definitions of AE-Related Terms

AE Severity:

Mild: Awareness of sign or symptom but easily tolerated.

Moderate: Discomfort sufficient to cause interference with normal activities.

Severe: Incapacitating, with inability to perform normal activities.

AE Relationship:

Related: A clinical event, including laboratory test abnormality, where there is a “reasonable possibility” that the SAE was caused by the study drug, meaning that there is evidence or arguments to suggest a causal relationship.

Probably: A clinical event, including laboratory test abnormality, with a reasonable time sequence to drug administration, unlikely to be attributed to concurrent disease or other drugs or chemicals, and which follows a clinically reasonable response on withdrawal.

Possibly: A clinical event, including laboratory test abnormality, with a reasonable time sequence to drug administration, but which could also be explained by concurrent disease or other drugs or chemicals. Information on drug withdrawal may be lacking or unclear.

Unrelated: This category is applicable to AEs which are judged to be clearly and incontrovertibly due to extraneous causes (diseases, environment, etc.) and do not meet the criteria for drug relationship listed for the above-mentioned conditions.

9.3 Clinical management of adverse events

9.3.1 Identification of adverse events by the investigator

AE monitoring and reporting will be followed-up until day 30±7. SAEs will be followed through the final study exit visit (day 90±14 visit or death or end of study whichever is sooner) or until the subject is deemed “lost to follow-up”.

AE identification while the subject is admitted to the acute stroke hospital will be collected via acute stroke hospital patient records and verbal histories from the subject or legally authorized representative (LAR). For follow up visits after discharge from the acute stroke hospital the subject (or LAR if the subject is not able to respond to the questions) will be asked about the occurrence of AEs since the last contact, and if available, from records at the acute stroke hospital. AEs that were ongoing at the last contact will be updated with a stop date or confirmed as ongoing. AE collection will continue until day 30±7, and SAE to day 90±14 or the final contact.

A consistent methodology of eliciting AEs at all subject evaluation timepoints will be used. Non-directive questions include: How have you felt since your last clinical visit/hospital discharge? Have you had any new or changed health problems since you were last here? Have you had any unusual or unexpected worsening of your underlying medical condition or overall health? Have there been any changes in the medicines you take since your last clinical visit/hospital discharge?

Diagnosis versus signs and symptoms for the purpose of AE reporting: if known at the time of reporting, a diagnosis should be reported rather than individual signs and symptoms. However, if a constellation of signs and/or symptoms cannot be medically characterized as a single diagnosis it is acceptable to report the information that is ultimately available.

9.3.2 Reporting of adverse events

AEs should be reported as they occur on the electronic CRF (e-CRF). Documentation must be supported by an entry in the subject's file. Each event should be described in detail along with start and stop dates, severity, relationship to investigational product as judged by the investigator, action taken and outcome.

9.3.3 Reporting of serious adverse events

In order to comply with current regulations on SAE reporting to health authorities, the investigator must document all SAEs regardless of causal relationship and notify the sponsor. The investigator will give access and provide the sponsor with all necessary information to allow the sponsor to conduct a detailed analysis of the safety of the investigational product. It is the responsibility of the investigator to request all necessary documentation (e.g., medical records, discharge summary, autopsy) in order to provide comprehensive safety information. All relevant information must then be transcribed into the e-SAE form.

9.3.4 Reporting by the investigator

All SAEs must be reported to the sponsor within 24 hours of the local investigator's first awareness of its occurrence. SAEs will be reviewed by the trial medical monitor. The investigator will report the SAEs using the e-SAE form in the e-CRF, which will send an immediate alert to the sponsor. If the e-CRF system is not available, a paper SAE form should be directed within 24 hours.

9.3.5 Reporting SAEs to the health authorities and ethics committees

The sponsor will inform the relevant health authorities of any reportable SAEs according to the local regulatory requirements. Reporting to the health authorities will be according to the sponsor's standard operating procedures.

SAEs that are assessed by the sponsor to be unexpected and related to study drug (expedited reporting SAEs) will be reported to the regulatory agencies as per country requirements. All other SAEs will be reported to regulatory agencies based upon local reporting requirements.

The sponsor's medical monitor or designee will notify the investigators in writing of the occurrence of any reportable SAEs. The sponsor or delegate will be responsible for reporting suspected unexpected serious adverse reaction to any Central EC in compliance with local current legislation. The investigators will be responsible for informing their local EC of any reportable SAEs as per their local requirements.

9.4 Data and safety monitoring board

To ensure the safety of the interventional procedures, an independent DSMB will monitor the trial. The independent DSMB will be composed of an experienced neurologist, an interventionalist, and a biostatistician, which are not involved in the trial. The DSMB will meet at least once a year, and is provided with structured unmasked reports, prepared by the trial statistician, for their reference only. DSMB is responsible for recommendations to the executive committee regarding stopping or extending the trial. In addition, the DSMB will review the occurrence of SAEs and make recommendations to the executive committee regarding safety of the trial.

In addition, interim analysis results, including mortality and other primary outcome data (e.g., SAEs attributed to treatment), will be confidentially shared with the DSMB chair. The DSMB will also review all accumulated safety data and conduct a single interim analysis when one-third (114 patients) of the primary endpoint follow-ups are completed. Based on the interim analysis, the DSMB may provide the BEST-BAO research team with recommendations for sample size adjustments, changes to the study design, or early termination of the trial if

necessary. These recommendations will be conveyed to the sponsor through the SC chair. If the sponsor decides not to fully implement the DSMB's recommendations, a rationale will be provided to the EC for review. Further details on DSMB procedures are outlined in the DSMB charter.

10. Statistical analysis

10.1 Sample size calculation

Currently, no large-scale RCTs exist in this field. The sample size calculation for this study is based on the results of the RESCUE-RE registry study in the Chinese population^[25], which reported that the proportion of patients achieving a mRS score ≤ 2 at 90 \pm 14 days post-procedure was 42.03% in the IVT followed by EVT group and 26.14% in the EVT alone group. Based on the superiority hypothesis, the study aims to determine whether the favorable outcome rate (90-day mRS ≤ 2) in the IVT followed by EVT group is superior to that in the EVT alone group. Assuming a one-sided type I error rate of 0.025 and 80% statistical power, and using a 1:1 randomization ratio, the required sample size is 136 patients per group (a total of 272 patients). Considering an anticipated dropout rate of approximately 20%, the final sample size is adjusted to 340 patients, with 170 patients per group.

This study hypothesizes that IVT followed by EVT is superior to EVT alone. However, given the limited reference data and clinical evidence in the anterior circulation indicating that EVT alone may be non-inferior to IVT followed by EVT, an interim analysis is planned after one-third (114) of the patients have completed follow-up for the primary endpoint. During the interim analysis, the DSMB will evaluate the efficacy data from both groups and conduct a sample size re-estimation based on the conditional power calculated from the available data. The DSMB will provide recommendations to the BEST-BAO research team on adjustments to the sample size or modifications to the study hypothesis.

If the efficacy advantage of the IVT followed by EVT group over the EVT alone group is less than anticipated, the sample size may be expanded appropriately, with an upper limit of no more than 20% of the original sample size. If the efficacy of the two groups appears to be similar, the study design will shift to a non-inferiority framework, evaluating whether EVT alone is non-inferior to IVT followed by EVT. Assuming similar efficacy (with both groups achieving a 90-day mRS score ≤ 2 in 42.03% of patients), the current sample size of 170 patients per group provides 80% power to test non-inferiority, with a one-sided type I error rate of 0.025 and a non-inferiority margin of -15%. The interim analysis and sample size re-estimation will be conducted under the strict control of the DSMB to ensure that the type I error rate is not inflated.

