In this context,  $p_T$  represents the proportion of patients in the IVT followed by EVT group achieving a 90-day mRS score of  $\leq 2$ , while  $p_C$  represents the proportion in the EVT alone group.  $\Delta$  denotes the non-inferiority margin, defined as a positive value. Assuming that the efficacy of the two groups is equivalent, with both achieving a 90-day mRS score of  $\leq 2$  in 42.03% of patients, and under the conditions of a one-sided type I error rate of 0.025 and a non-inferiority margin of -15%, the current sample size of 170 patients per group provides 80% power to detect non-inferiority.

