##### 3.1.2 Modified intention-to-treat population (m-ITT)

The m-ITT population includes all randomized subjects who received either IVT followed by EVT or EVT alone treatment. The analysis will be conducted based on their randomized treatment groups following the intention-to-treat principle.

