## 3.4 Interim Analysis

An interim analysis is planned once 1/3 (114 subjects) of the total population has completed the follow-up for the primary endpoint. During this interim analysis, the DSMB will conduct a sample size re-estimation based on the efficacy data obtained from both groups.

If the efficacy advantage of the IVT followed by EVT group over the EVT alone group is less than anticipated, the sample size will be appropriately increased. The DSMB will calculate the **conditional power** from the current data and provide recommendations to the BEST-BAO research team regarding sample size adjustments or modifications to the study hypothesis. The maximum increase in sample size will not exceed 20% of the original planned sample size.

If the efficacy of the two groups is found to be similar, the study hypothesis will be adjusted to a **non-inferiority hypothesis** to determine whether EVT alone is non-inferior to IVT followed by EVT. Assuming both groups achieve similar efficacy, with 42.03% of patients achieving a 90-day mRS  $\leq 2$ , and with a one-sided type I error rate of 0.025 and a non-inferiority margin of -15%, the current sample size of 170 patients per group will provide 80% power to demonstrate non-inferiority.

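### The 80% non-inferiority power counts all 170 per arm as analysed, while the 80% superiority power allows for about 20% dropout; the documents neither say so nor define the 20%

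*Protocol*

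**What the plan says.** Protocol 10.1 takes rates of 42.03% (IVT followed by EVT) and 26.14% (EVT alone), one-sided alpha 0.025 and 80% power, and arrives at 136 per arm. It continues: "Considering an anticipated dropout rate of approximately 20%, the final sample size is adjusted to 340 patients", which is 170 per arm.

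If the arms look similar at the interim analysis, the trial moves to a non-inferiority test of EVT alone. For that case the section says "the current sample size of 170 patients per group provides 80% power to test non-inferiority", assuming 42.03% in both arms, one-sided alpha 0.025 and a margin of 15 percentage points. The Protocol Summary and Protocol 4.5 repeat this. SAP 1.5 says "the current sample size of 170 patients per group provides 80% power to detect non-inferiority" and SAP 3.4 says "the current sample size of 170 patients per group will provide 80% power to demonstrate non-inferiority". None of the five places mentions loss in connection with the non-inferiority figure.

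Four provisions bear on who is analysed:

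- SAP 3.1.2: "The m-ITT population includes all randomized subjects who received either IVT followed by EVT or EVT alone treatment". Randomised but untreated patients are therefore outside the primary analysis set.
- SAP 3.2.3: within m-ITT every patient gets a 90-day mRS. Deaths score 6, known survivors with a missing value have their last value carried forward, and unknown vital status scores 6.
- Protocol 8.2: "patients cannot be excluded from the study after the allocation is revealed".
- Protocol 8.4: "Data from patients who do not provide consent for further participation will be anonymized and used for baseline analysis", but also "Missing data, including the final mRS score, will be addressed using statistical methods during analysis".

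**The concern.** The same 170 serves as a recruitment target for superiority, with 136 expected to be analysed, and as an analysed number for non-inferiority. A reader who sees two 80% figures a few lines apart, after a sentence on 20% dropout, will assume that both allow for it in the same way. They do not.

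A switch to non-inferiority after the interim analysis would rest on this one power figure, since no other is given. The reader also cannot work out how far it might fall, because the plan never says whether the 20% means untreated patients, patients who refuse further participation, or patients with a missing 90-day mRS. These groups are handled differently and have different effects on the test.

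**Working it through.** **Inputs.** From Protocol 10.1: rates 0.4203 and 0.2614 for superiority; 0.4203 in both arms and margin 0.15 for non-inferiority; one-sided alpha 0.025 (z = 1.96); power 80% (z = 0.8416); dropout 20%; 1:1 allocation.

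**The plan's figures reproduced** (unpooled variance):

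- Superiority: (1.96 + 0.8416)² × (0.4203 × 0.5797 + 0.2614 × 0.7386) / 0.1589² = 135.76, so 136 per arm; 136 / 0.8 = 170.
- Non-inferiority: (1.96 + 0.8416)² × 2 × 0.4203 × 0.5797 / 0.15² = 169.99, so 170 per arm with nothing added for loss.

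**Non-inferiority power by number analysed.** Power = Φ(0.15 / √(2 × 0.4203 × 0.5797 / n) − 1.96).

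| Analysed per arm | Loss from 170 | Formula above | Farrington-Manning | Exact enumeration, Wald rule |
|---|---|---|---|---|
| 170 | none | 80.0% | 80.6% | 79.7% |
| 161 | about 5% (assumed) | 77.8% | 78.4% | 77.3% |
| 153 | 10% (assumed) | 75.7% | 76.4% | 76.0% |
| 136 | 20% (all of the plan's dropout) | 70.7% | 71.4% | 71.0% |

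By the same unpooled formula, superiority power is 80.1% at 136 and 88.0% at 170.

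**If the patients stay in and are scored mRS 6.** Suppose a share f of each arm is counted as failures, with 170 per arm analysed. Each rate is multiplied by (1 − f).

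- f = 20% (extreme assumption): the superiority rates become 0.3362 and 0.2091, and superiority power falls to 75.8%. With both rates at 0.3362, nominal non-inferiority power rises to 83.3%.
- f = 10% (assumption): superiority 82.5%, non-inferiority 81.4%.

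**Type I error on that route.** Use the protocol's direction (EVT alone tested against IVT followed by EVT) and put the truth on the margin: 0.4203 and 0.2703, with 170 per arm. The expected difference shrinks from 0.15 to 0.15(1 − f). The one-sided error is Φ((0.15 − 0.15(1 − f)) / SE − 1.96), with SE computed from the diluted rates.

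| Share scored as failures in both arms (assumed) | One-sided error |
|---|---|
| 0% | 2.5% |
| 2% | 2.9% |
| 5% | 3.5% |
| 10% | 4.9% |

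Exact enumeration gives the same values. There is no inflation if the imputed values preserve the true difference.

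**The case against.** The strongest reply is that no stated figure is wrong. The 136, the 170 and the 80% all reproduce, and no two passages contradict each other, so this is an unstated assumption rather than an error. That stands.

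The reply continues that SAP 3.2.3 keeps treated patients with a missing mRS in the analysis, so only untreated patients clearly leave m-ITT. Protocol 8.4 leaves some doubt about patients who refuse further participation. If an assumed 2% were untreated, about 166 to 167 per arm would remain and power would be about 79%. This also stands, and it rules out three stronger readings that a reader might draw:

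- That the number analysed lies somewhere between 136 and 170. The lower end is not derived from any provision; it requires the whole 20% to leave m-ITT, and no passage says that will happen.
- That only the superiority figure is protected against dropout. On the imputation route the reverse can occur: with 20% scored mRS 6, superiority falls below 80% and nominal non-inferiority power rises.
- That the trial needs 170 / 0.8 = 213 per arm. This again assumes that the whole 20% leaves the analysis.

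Covariate adjustment could also help, because SAP 3.9.1 decides on the adjusted risk difference. A variance reduction of about 5%, 10% or 20% would restore 80% at 161, 153 or 136. The plan claims no such gain.

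Finally, dilution is a question of bias and not of power, and it concerns different patients, since someone imputed as mRS 6 has not left the analysis. Telephone and proxy interviews (Protocol 8.1.5) make the larger assumed shares less likely. This is why the dilution point is secondary here.

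What the reply does not answer is the purpose of the inflation. If imputation keeps nearly everyone in, the plan does not explain what the 20% is for. If the 20% does leave, the non-inferiority power is overstated.

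**Conclusion.** The point holds as a fault of disclosure and definition, and should be fixed. The 80% non-inferiority power assumes 170 analysed per arm with no loss. The neighbouring 80% for superiority assumes 136 analysed. The documents do not disclose the difference or define the 20%.

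The size depends on what the 20% means. If all of it leaves the analysis, non-inferiority power is about 71%, some 9 points below the stated value. If it stays in through SAP 3.2.3, nominal power remains near 80% or slightly higher. In that case scoring unknown vital status as mRS 6 in both arms pulls the difference toward zero, which favours non-inferiority and lowers superiority power. The error rates of 2.9%, 3.5% and 4.9% rest on assumed shares of 2%, 5% and 10%.

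The power figures are unadjusted and use the plan's common rate of 42.03%. The alternative formulas in the table agree within about one point.

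**What to change.** 1. In the Protocol Summary, Protocol 4.5, Protocol 10.1, SAP 1.5 and SAP 3.4, state that the 80% non-inferiority power assumes 170 per arm analysed with no loss. Say which patients the 20% covers: untreated, withdrawn, or missing the 90-day mRS. Restate the power on that basis: about 71% if all 20% leave the analysis. Intermediate values (about 78% at 5% loss, 76% at 10%) should be labelled as assumptions, not as expected numbers. If a gain from covariate adjustment is relied on, give its assumed size.

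2. Prespecify one sensitivity analysis for the non-inferiority test. One option is multiple imputation by arm from baseline covariates and the day 5–7 and day-30 mRS, which Protocol 8.1.5 already collects, with known deaths kept at mRS 6. Report it beside the primary result and not as a second condition for success.

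The cost is a less favourable power statement at five places and one extra analysis to program. The number randomised, the primary missing-data rule and the success criterion do not change.
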